## **4. GENERAL DEFINITIONS AND NAMING CONVENTIONS**

In order to avoid ambiguity during the analysis, a number of definitions and conventions for data handling are described here.

### **4.1 General Methodology and Presentation of the Results**

The default summary statistics for quantitative (continuous) variables will be

- the number of patients with data at the visit (n),
- number of patients with missing data (nmiss),
- mean,
- standard deviation (SD),
- median,
- first quartile (Q1) and third quartile (Q3)
- minimum (min) and maximum (max)

for patients with data.

Mean, median, and the quartiles will be presented to one more decimal place than the raw value. The minimum and maximum values will be presented with the same decimal precision as the raw value. SD will be reported to two decimal places greater than the original value.

For qualitative (categorical) variables, the number (n) and percentage (%) of patients with non-missing data per category will be the default frequency tabulations. Where appropriate and present, the number of missing values will be displayed as “Missing” category.

Percentage values are to be presented to one decimal place, for example, 52.3%.

The denominator used for calculation of the percentages will be specified in a footnote to the tables for clarification.

All reported p-values will be two-sided. No adjustment for multiplicity will be performed.

### **4.2 Statistical Output Layout**

All titles and column headers (consisting of one or several words) will be capitalised; articles, prepositions, and conjunctions, and “to” in infinitives will not be capitalised, except they are at the beginning of titles or headers.

All pages will be numbered according to the table/listing/figure to which the page belongs to. Every table/listing/figure will be numbered from page 1, “Page X of Y” at the bottom of each page.

The definition of baseline and endpoint value will be described in a footnote in every TLF where applicable. Other important definitions will also be presented if necessary.

Dates will be listed in the format: yyyy-mm-dd (e.g. 2003-11-20). Times will be listed in the format: hh:mm (e.g. 13:15) or in the format hh:mm:ss if seconds are collected. When date and time are collected, these are listed in the format: yyyy-mm-ddThh:mm (e.g. 2003-11-20T09:15), yyyy-mm-ddThh, or yyyy-mm-ddThh:mm:ss.

Partial missing dates will be listed in the format yyyy-mm (e.g. 2013-11) if only day is missing or in the format yyyy (e.g. 2013) if month and day are missing.

Missing data including missing dates or times will be displayed in listings as blank fields, unless otherwise specified.

Listings will be sorted by treatment group, patient number and visit number where applicable, unless specified otherwise.

### **4.3 Treatment Group Names and Labels**

Statistical output will be presented by treatment group and the treatment labels to be used in the tables, listings and figures are defined in Table 1 below.

**Table 1: Treatment Group Labels**

Number	Description	Label in TLFs
1	One or half of 800 mg ESL tablet once daily	ESL
2	One or half of placebo tablet once daily	Placebo

#### **4.4 Visit Names and Labels**

The names to be used in the analysis datasets and the labels to be used in the tables, listings and figures for the different study visits are defined in Table 2 below.

**Table 2: Visit Labels**

Name	Description	Label in TLFs
Visit 1a	Screening/baseline, within 120 hours after stroke, or since last time seen well	V1a
Visit 1b	Day 1, within 120 hours after stroke, or since last time seen well	V1b
Visit 2	Day $8 \pm 2$	V2
Visit 3	Day $38 + 4$	V3
Visit 4	Day $85 \pm 10$	V4
Visit 5	Day $183 \pm 10$	V5
Visit 6	Day $267 \pm 10$	V6
Visit 7	Day $365 \pm 10$	V7
Visit 8	Day $449 \pm 10$	V8
EoT	Day $547 \pm 10$	EOT
EDV	Early discontinuation visit	EDV
UNS	Unscheduled visits	USV X.X

#### **4.5 Visit Slotting**

Due to COVID-19 pandemic visits might be delayed. Therefore, visit slots will be used for the analysis of efficacy (where applicable) and safety variables (where applicable). For a visit slot the closest non-missing assessment in time (scheduled or unscheduled) to the target day will be used (see Table 3).

**Table 3: Visit Slotting**

Visit Slot/ Label	Target Day	Description
V1a	-	Screening/baseline, within 120 hours after stroke, or since last time seen well
V1b	1	Day 1, within 120 hours after stroke, or since last time seen well
V2	8	Closest non missing assessment to target day between study day 2 and 31
V3	38	Closest non missing assessment to target day between study day 32 and 71
V4	85	Closest non missing assessment to target day between study day 72 and 171
V5	183	Closest non missing assessment to target day between study day 172 and 242
V6	267	Closest non missing assessment to target day between study day 243 and 353
V7	365	Closest non missing assessment to target day between study day 354 and 437
V8	449	Closest non missing assessment to target day between study day 438 and 533
EOT	547	Closest non missing assessment to target day between study day 534 and >547

EDV	EDV	Early discontinuation visit
-----	-----	-----------------------------

If, for any variable, a visit was not scheduled (e.g. V4 for vital signs), the respective measurement will be assigned to the visit slot with the closest target day where a visit was scheduled. If two measurements fall into that slot, the closest one to target day will be used.

If, for any safety variable, V1b is not scheduled and a measurement is taken on Study Day 1, this measurement will be slotted to V2 if the assessment was done after first IMP intake.

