#### **4.6 Study Day Numbering**

All assessment dates will be related to the date of first IMP intake. The date of first IMP intake is referred to as Day 1. Day -1 is the day preceding Day 1 and Day 0 will not be defined. The numbering is such that Day -2 is the day before Day -1, Day 2 is the day after the first IMP intake, etc.

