#### **5.4.2 Compliance**

Overall treatment compliance will be calculated as:

$$\text{Overall compliance (\%)} = \frac{\text{Number of IMP tablets taken}}{\text{Number of IMP tablets the patient should have taken}} \times 100$$

The number of IMP tablets taken and the number of IMP tablets the patient should have taken will be collected in eCRF. The “Number of IMP tablets taken” will be calculated by “Dispensed Amount of Tablets” – “Returned Amount of Tablets”.

In case an IMP bottle is not returned, the overall compliance will be considered as missing.

All patients with a compliance <80% and >120% will be discussed at BDRM. It was decided during BDRM that all patients with a treatment duration > 4 days are compliant, as this is the very minimum amount of intakes to reach steady state serum level of ESL. Patients with missing compliance were discussed at BDRM and compliance was assessed on a case-by-case basis.

The following statistical output will be provided:

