**Table 15.3.2.6 Signs of Hyponatraemia – Safety Set**

Number and frequency of patients will be presented by sodium level categories and by visit. This table will be provided by treatment group and in total. Visit Slots will be used.

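### SAP 4.5 lets a first-dose-day safety value stand as the V2 result when V2 is late (Days 16-31) or missing, which can mislabel some by-visit safety tables

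*SAP*

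**What the plan says.** SAP 4.5 introduces visit slots with the remark "Due to COVID-19 pandemic visits might be delayed" and then sets the general selection rule: "the closest non-missing assessment in time (scheduled or unscheduled) to the target day will be used". In Table 3 the V2 row has target Day 8 and the description "Closest non missing assessment to target day between study day 2 and 31".

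Two paragraphs follow the table. The first covers variables not assessed at a given visit. Their values go to the nearest target day at which the variable was scheduled, and "If two measurements fall into that slot, the closest one to target day will be used". The second covers safety variables with no V1b assessment and a measurement on Study Day 1: "this measurement will be slotted to V2 if the assessment was done after first IMP intake". SAP 4.6 fixes the origin: "The date of first IMP intake is referred to as Day 1".

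The schedules of procedures and SAP 5.6.2 to 5.6.5 show that laboratory tests, urinalysis, ECG, vital signs and examinations are not scheduled at V1b. The Day 1 sentence therefore reaches all of them.

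**The concern.** The Day 1 sentence puts into the V2 slot a value that the slot's own window excludes, and the nearest-to-target rule then lets it compete with a real V2. Slots exist to absorb delayed visits, yet a delayed V2 is exactly the one that loses. The SAP's own benchmark shows how far apart the two values are: SAP 5.4.2 accepts as compliant a treatment duration of more than 4 days, "as this is the very minimum amount of intakes to reach steady state serum level of ESL". A value taken hours after one dose is not comparable with one taken in the second to fourth week of dosing.

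V2 matters because it is the only scheduled visit with these assessments during full dosing. IMP ends on Day 30 for half-tablet patients and on Day 37, after a taper from Day 31, for one-tablet patients. SAP Table 2 prints V3 as Day 38 + 4, while the SAP schedule prints 38 ± 4. These should be reconciled, but on either printing V3 falls no earlier than Day 34, after full dosing has ended. A first-dose value labelled V2 would pull the ESL column towards baseline in tables read for on-treatment effects. One example is Table 15.3.2.6, for which "Number and frequency of patients will be presented by sodium level categories and by visit".

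**Working it through.** There is no plan figure to reproduce. The check is a comparison of distances from the target day.

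**Inputs.** V2 target Day 8 and slot Days 2-31 (SAP Table 3); planned V2 window Day 8 ± 2, i.e. Days 6-10 (SAP Table 2); Day 1 = first IMP intake (SAP 4.6).

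**Formula.** Distance = |study day − 8|; the smallest distance is kept.

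| Day of the actual V2 | Distance | Against Day 1 (distance \|1 − 8\| = 7) | Number of days |
|---|---|---|---|
| 2-14 | 0 to 6 | V2 kept | 13 |
| 15 | 7 | tie, no rule | 1 |
| 16-31 | 8 to 23 | Day 1 kept | 16 |

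The rows add to 13 + 1 + 16 = 30 slot days. A V2 inside Days 6-10 is at most 2 days from target, so it always wins. Displacement needs a V2 at least 16 − 10 = 6 days past its planned window. If the slot holds no Day 2-31 value, the Day 1 value fills it.

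**Illustration for one patient (hypothetical values).** Sodium is 139 mEq/L after the dose on Day 1 and 126 mEq/L at a V2 on Day 17. Distances are 7 and 9, so the V2 entry is 139, in the category ≥ 135. The minimum post-baseline value is 126, in the category 125 to < 130.

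**Illustration for the ESL arm (all inputs assumed).** The documents give neither the share f of V2 values replaced nor any rate of low sodium. Suppose 10% on treatment and 2% on Day 1. The displayed rate is 0.10(1 − f) + 0.02f:

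- f = 2%: 9.84%
- f = 5%: 9.60%
- f = 10%: 9.20%

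Per 100 ESL patients, the planned arm size, that is 0.16, 0.40 or 0.80 of a patient. Recruitment stopped early (SAP 2.6 and 8), so the actual number would be smaller.

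**Where the V2 slot is used.** By-visit laboratory abnormalities, urinalysis and sodium categories (5.6.2), vital signs (5.6.3), ECG (5.6.4) and examinations (5.6.5). The laboratory summary tables name V1, baseline, V3, EDV and Endpoint, not V2. Adverse events are not slotted.

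**The case against.** **The text may mean less.** Table 3 opens V2 on Day 2, so the Day 1 sentence could be a fallback for an empty slot only. That reading is sensible, but nothing states it, and the general rule at the start of 4.5 applies to every slot. As written, Day 1 competes. Even as a fallback, a first-dose value would be labelled V2.

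**The trigger is narrow.** It takes a post-dose Day 1 value, a V2 on Day 16 or later or none at all, and no other value nearer Day 8. Screening values should precede dosing, because eligibility is confirmed before randomisation and the V1a eGFR sets the dose. Post-dose Day 1 values would therefore mostly be unscheduled. This stands. Against it, V1a and V1b may share a day, and the revision history shows that the rule entered at Draft 0.5, after the Blind Data Review Meeting. That suggests such values exist but does not prove it.

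**Much is backed up.** This largely stands for laboratory values. SAP 5.6.2 classifies patients by minimum post-baseline sodium, provides worst-post-baseline shift tables for haematology, biochemistry and coagulation, and lists patients with signs of hyponatraemia. A reader might infer that a low sodium could vanish from the report; the documents do not support that. The protection is partial, since the one table of sodium categories is specified by visit. Vital signs and ECG have listings but no worst-value table.

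**Days 2-4 look just as early.** A reader might infer that the V2 slot should open on Day 5. The documents do not support this: the 4-day figure is a compliance criterion, and a Day 5 opening would discard genuine on-drug values that Table 3 admits.

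**Conclusion.** The defect is real but minor. As written, a Day 1 post-dose safety value outranks a V2 on 16 of the 30 slot days, ties on one with no rule, and stands alone if V2 is missing. The mislabelled result would tend to dilute any ESL effect in the affected by-visit tables.

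The documents do not support reading this as a material bias in the trial's safety conclusions. The frequency is unknown and probably low, a V2 on Days 6-10 is untouched, and the assumed scenarios shift the displayed rate by less than one patient per 100. SAP 5.6 plans no between-arm test of these variables, and efficacy is not involved. The dilution also assumes that any ESL effect is smaller after one dose than after continued dosing. The point merits consideration, mainly for vital signs and ECG, where only listings would reveal a displaced value.

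**What to change.** Replace the Day 1 sentence in SAP 4.5 with a statement that safety measurements taken on Day 1 after the first intake are not eligible for the V2 slot. Say explicitly that this overrides the general rule sending unscheduled-visit values to the nearest scheduled target day. Deleting the sentence alone may not work, because V1a has no target day in Table 3 and that rule could send Day 1 to V2 again.

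At minimum, state that a Day 1 value never displaces a Day 2-31 value. Displacement then falls from 16 of 30 slot days to none, though an empty slot would still be filled by Day 1.

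Keep the Day 1 post-dose values in the listings and in the worst-post-baseline, minimum-sodium and safety-endpoint derivations, so that no data are lost. Leave the V2 slot opening on Day 2.

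The cost is one SAP sentence and one line of slotting code before unblinding. The downside is that a few patients may have a missing V2 value where a Day 1 value would have been shown.

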#### **4.6 Study Day Numbering**

All assessment dates will be related to the date of first IMP intake. The date of first IMP intake is referred to as Day 1. Day -1 is the day preceding Day 1 and Day 0 will not be defined. The numbering is such that Day -2 is the day before Day -1, Day 2 is the day after the first IMP intake, etc.

#### **4.7 Study Periods for primary and secondary efficacy analysis**

##### **Treatment Period**

The period from Day 1 to Day of last IMP intake will be defined as the treatment period.

##### **1-month-period!**

The period from Day 1 to Day 30 (Day 30 included) is defined as the 1-month-period.

##### **3-month-period**

The period from Day 1 to Day 91 (Day 91 included) is defined as the 3-month-period.

##### **6-month-period**

The period from Day 1 to Day 182 (Day 182 included) is defined as the 6-month-period.

##### **9-month-period**

The period from Day 1 to Day 273 (Day 273 included) is defined as the 9-month-period.

##### **12-month-period**

The period from Day 1 to Day 365 (Day 365 included) is defined as the 12-month-period.

##### **15-month-period**

The period from Day 1 to Day 456 (Day 456 included) is defined as the 15-month-period.

##### **18-month-period**

The period from Day 1 to Day 547 (Day 547 included) or EOT (scheduled visit) is defined as the 18-month-period.

#### **4.8 Baseline and Endpoint Value**

##### **Baseline value**

The baseline value for efficacy variables (BI, PHQ-9) is defined as value collected at visit V1a (within 120h after stroke). For the NIHSS score the worst value post-stroke until V1b will be defined as baseline.

The baseline value for all other variables is defined as the last non-missing value collected before the first IMP intake.

For EEG subgroup, the baseline values and the exploratory analysis will be defined in a separate report.

## **Endpoint value**

The endpoint value for an efficacy variable is defined as the last non-missing value collected after first intake of IMP before or at the respective endpoint (within the time window of interest i.e. 6 month-period, 12 month-period and 18 month-period).

The endpoint for a safety variable is defined as the last non-missing value collected after first intake of IMP that is no baseline value.

**Absolute change from baseline** will be calculated as

$$\text{Absolute Change from Baseline at Visit } X = \text{Value at Visit } X - \text{Baseline Value}$$

**Relative change from baseline (%)** will be calculated as

$$\text{Relative Change from Baseline at Visit } X = \frac{\text{Value at Visit } X - \text{Baseline Value}}{\text{Baseline Value}} \times 100$$

Note: Patients with a baseline value of '0' will be excluded from the calculation of relative change.

See section 5.4.1 for the definition of first and last IMP intakes.

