This is a multicentre, double-blind, randomised, placebo-controlled, parallel-group trial in patients with acute intracerebral haemorrhage with a CAVE score \geq 3 or an acute ischaemic stroke with a SeLECT score \geq 6.

At the first visit (screening/baseline, V1a), patients will undergo several examinations to check eligibility. The next visit (V1b) has to be performed within 96 hours after primary stroke occurrence. After eligibility has been confirmed, patients will be randomised (randomisation ratio 1:1) to treatment with ESL 800 mg (Group A) or placebo (Group B). Patients can receive therapies for stroke treatment according to local clinical practice at any time during the trial.

Patients will start treatment with the investigational medicinal product (IMP), i.e. ESL or placebo, within 96 hours after primary stroke occurrence at V1b. They will continue treatment until Day 30 after randomisation and then be tapered off. Thereafter, patients will be followed up until 18 months after randomisation. Patients can concomitantly receive antiepileptic therapies, except commercially available ESL or oxcarbazepine, until Day 30. Concomitant antiepileptic therapies have to be discontinued and down-titration has to be started according to the respective Summary of Product Characteristics (SmPC). If the antiepileptic drugs (AEDs)/benzodiazepine are not already discontinued before, down-titration must be started on Day 31 at the latest.

If one or more AS(s) occur(s) within 7 days after primary stroke, this will not result in change of IMP dose. Patients having a first US will discontinue IMP treatment and will be treated at the discretion of the investigator until 18 months after randomisation, except with commercially available ESL.

Further visits will be performed 7 days (V2, on-site), 37 days (V3, on-site), 12 weeks (V4, telephone), 26 weeks (V5, on-site), 38 weeks (V6, telephone), 52 weeks (V7, on-site), 64 weeks (V8, telephone) and 78 weeks (End of Trial [EoT] visit, on-site) after V1b. Patients

who discontinue trial participation prematurely will be asked to come to the site for an early discontinuation visit (EDV). Unscheduled visits (UNS) will be performed at the discretion of the investigator, as necessary.

Patients or their caregivers (as applicable) will be instructed to contact the site immediately after a seizure has occurred and to document seizure information in the patient diary.

Number of patients (planned):

Screened:	220
Randomised:	200

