#### **2.1.2 Secondary Objectives**

The secondary objectives of this trial are:

1. To assess if ESL treatment (started within 120 hours after stroke occurrence and continued for 30 days) changes the incidence of USs – within the first 12 months after randomisation as compared to placebo
2. To assess if ESL treatment (started within 120 hours after stroke occurrence and continued for 30 days) changes the incidence of USs during the course of the trial – until 18 months after randomisation as compared to placebo
3. To assess the number of acute symptomatic seizures (Ass)

To assess the effect of ESL treatment over 18 months follow-up period on:

4. Time to first US after randomisation
5. Number of Uss
6. Functional outcome, assessed by Barthel Index original 10-item version (BI)
7. Functional outcome, assessed by National Institutes of Health Stroke Scale (NIHSS)
8. Post-stroke depression, assessed by Patient Health Questionnaire (PHQ-9)
9. Overall survival

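### The exploratory comparisons of BI, NIHSS and PHQ-9 leave the collected baseline score unused; a baseline-adjusted comparison at Endpoint would be a cheap improvement, and section 4.8 should say that this Endpoint is the 18-month value

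*SAP*

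**What the plan says.** **Comparisons.** SAP 5.5.2.5 (BI), 5.5.2.6 (NIHSS) and 5.5.2.7 (PHQ-9) plan exploratory two-group comparisons by Wilcoxon-Mann-Whitney test with Hodges-Lehmann intervals. The BI code analyses change from baseline with treatment as the only factor. No code is given for NIHSS or PHQ-9, and no baseline covariate appears for any of the three. Baseline scores are collected and defined in section 4.8: V1a for BI and PHQ-9, the worst post-stroke value up to V1b for NIHSS. Section 4.1 states that p-values are not adjusted for multiplicity.

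**Endpoint.** Section 4.8 defines the efficacy Endpoint as the last non-missing value after first IMP intake, "before or at the respective endpoint (within the time window of interest i.e. 6 month-period, 12 month-period and 18 month-period". Section 4.7 sets those periods:
- 6 months: "The period from Day 1 to Day 182 (Day 182 included) is defined as the 6-month-period".
- 12 months: "The period from Day 1 to Day 365 (Day 365 included) is defined as the 12-month-period".
- 18 months: "The period from Day 1 to Day 547 (Day 547 included) or EOT (scheduled visit) is defined as the 18-month-period".

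Table 2 of the SAP allows V5 on Day 183 ± 10, V7 on Day 365 ± 10 and EoT on Day 547 ± 10. The by-visit rows follow Table 3 instead. For V5 that is "Closest non missing assessment to target day between study day 172 and 242", and for V7 "Closest non missing assessment to target day between study day 354 and 437".

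**The concern.** In a randomised comparison of a follow-up score, the baseline score is usually the most useful covariate available. Subtracting it is not the same as adjusting for it: a change score is efficient only when follow-up tracks baseline with a slope near 1. If the slope is lower, part of the baseline variation stays in the analysis as noise. Recruitment also stopped before the planned sample size was reached (SAP 2.6), so precision is worth having.

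The second matter is which value is compared. Section 4.8 names three periods and does not assign one to these scales. Only the 18-month period has an allowance for a scheduled visit. If someone derived a 6- or 12-month Endpoint literally, patients seen on schedule but after the cut-off would be represented by a much older score, depending only on their visit date.

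Both matters concern exploratory comparisons of secondary endpoints. The primary and secondary failure rates are not touched.

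**Working it through.** **1. What adjustment can gain**

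Let r be the follow-up SD divided by the baseline SD, and ρ the baseline to follow-up correlation. Neither is in the documents. In units of the follow-up variance, for normal scores:

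- change score: 1 + 1/r² − 2ρ/r
- baseline-adjusted: 1 − ρ²
- difference: (1/r − ρ)², never negative and zero only when ρ × r = 1

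Examples:
- r = 0.75, ρ = 0.3: 1 + 1.778 − 0.800 = 1.978, against 0.910.
- r = 1, ρ = 0.5: 1 + 1 − 1 = 1.00, against 0.75.
- r = 1.25, ρ = 0.8: 1 + 0.64 − 1.28 = 0.36, against 0.36.

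The table shows simulated power of Wilcoxon on change / rank-ANCOVA (Quade). All settings are assumed: bivariate normal scores, 50 per arm, shift 0.4 follow-up SD, two-sided 5%, 2,000 runs per cell, Monte Carlo standard error about 1 point.

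| SD ratio r | ρ = 0.3 | ρ = 0.5 | ρ = 0.8 |
|---|---|---|---|
| 0.75 | 0.27 / 0.51 | 0.34 / 0.59 | 0.68 / 0.86 |
| 1 | 0.38 / 0.50 | 0.49 / 0.61 | 0.85 / 0.86 |
| 1.25 | 0.44 / 0.52 | 0.57 / 0.60 | 0.90 / 0.87 |

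The differences run from +25 to −3 points. A repeat with 8,000 runs per cell agreed with every entry to within 3 points.

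The same grid at 25, 50 and 100 per arm gave these extremes:
- Largest gain: about 31 or 32 points (0.50 against 0.82 at 100 per arm, r = 0.75, ρ = 0.3).
- Largest loss: about 2 to 4 points (0.61 against 0.57 at 25 per arm, r = 1.25, ρ = 0.8, where ρ × r = 1).

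With Barthel-like scores, rounded to steps of 5 and bounded at 0 and 100, rank-ANCOVA gained in every cell.

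Under no effect with normal scores (r = 1, 4,000 runs), rejection rates were 0.049-0.054 for Wilcoxon and 0.051-0.053 for rank-ANCOVA. With the bounded scores they were about 4% to 7%.

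**2. The Endpoint windows**

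Target day = 1 + 7 × weeks after V1b. This gives 183 for V5 (26 weeks), 365 for V7 (52) and 547 for EoT (78), reproducing Table 2.

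| Visit | Permitted days | Period ends | Permitted days after the end |
|---|---|---|---|
| V5 | 173-193 | 182 | 183-193: 11 of 21, target day included |
| V7 | 355-375 | 365 | 366-375: 10 of 21 |
| EoT | 537-557 | 547, or scheduled EOT | 0 of 21 (10 of 21 without the EOT clause) |

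The protocol schedule is "37 days (V3, on-site), 12 weeks (V4, telephone), 26 weeks (V5, on-site), 38 weeks (V6, telephone), 52 weeks (V7, on-site". The telephone contacts V4 and V6 do not collect these scales. The replacement would therefore be V3, 183 − 38 = 145 days older than V5, or V5, 365 − 183 = 182 days older than V7, unless an unscheduled score exists.

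**3. Which period the documents point to**

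- SAP 2.1.2 frames the objectives for these scales with the words "To assess the effect of ESL treatment over 18 months follow-up period on".
- Each table has a single Endpoint row. In the comparison tables it follows V7, and there is no EOT row.
- Section 10.1 lists no 6- or 12-month table for these scales.

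On the 18-month reading, the latest compliant V5 (Day 193) and V7 (Day 375) both precede Day 547. A scheduled EoT on Days 548-557 is covered by the clause in section 4.7, taking it to mean the actual date of that visit. No on-schedule visit is lost.

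**The case against.** **Against the adjusted comparison.** The protocol synopsis plans only descriptive statistics for these scales, so the SAP already goes further than required. The planned tests are valid, and asking for another is partly preference. It adds p-values that nobody adjusts. The size of the gain rests on assumed values for the correlation, SD ratio, arm size and shift. At 50 per arm with a shift of 0.6, for example, one run gave 0.53 against 0.87. The scales are also bounded sums rather than normal variables.

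Most of this stands, and it is why the point is an improvement. The normality and arm-size objections carry less weight: bounded, stepped scores at 25, 50 and 100 per arm still showed a gain throughout. NIHSS-like and PHQ-9-like distributions were not simulated separately.

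A reader might infer that the unadjusted comparisons are biased or invalid. They are not: randomisation protects them, and their simulated false-positive rate is close to 5%.

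**On the Endpoint.** A reader might infer that about half of the compliant V5 or V7 visits are lost from planned analyses. The documents do not support this. The counts are calendar days rather than patients, no listed output uses a 6- or 12-month Endpoint for these scales, and every compliant V5 and V7 falls inside its Table 3 slot. Section 4.8 is a general rule for efficacy variables, so naming three periods does not by itself plan three Endpoints. The SAP also promises the endpoint definition in footnotes (4.2), and its table shells are separate attachments that may settle the matter. What remains is that no section of the SAP states the period.

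**Conclusion.** The main point holds as an optional improvement to exploratory analyses. Adding a baseline-adjusted comparison uses data already collected. Over the assumed grid it changes power by anything from a loss of about 2 to 4 points to a gain of about 31 or 32. It is near zero or slightly negative only where the correlation times the SD ratio is close to 1. The actual gain cannot be stated, because the correlation, SD ratio, effect and final sample size are not in the documents.

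The Endpoint matter is a minor clarification. The 18-month reading is an inference, but a well-supported one, and on it nothing on schedule is lost. The loss on Days 183-193 or 366-375 arises only if someone derives a 6- or 12-month Endpoint literally. The share of patients affected in that case is unknown, because the documents contain no visit dates.

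**What to change.** 1. In SAP 5.5.2.5 to 5.5.2.7, add one baseline-adjusted comparison per score at Endpoint, for example rank-ANCOVA. Label it exploratory and place it beside the planned Wilcoxon and Hodges-Lehmann output, which stays as it is. The cost is one extra model per score, that is three more p-values without multiplicity adjustment. No new data are needed. It should be specified before unblinding.

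2. In section 4.8, state that Endpoint for BI, NIHSS and PHQ-9 is the 18-month value, and remove the 6- and 12-month windows for these scales. Repeat this in the endpoint footnote that section 4.2 already promises. The cost is one clause. The failure-rate periods in section 4.7 and the Table 3 slots should stay unchanged.
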